91 largely been ignored by the literature. Due to the magnitude of the problem of obesity,
92 and the potential benefits of exercise with this population, it is important to determine the
93 elements of a feasible and effective physical activity program.

94

95 **SPECIFIC AIMS AND SCOPE OF THE PROPOSED RESEARCH**

96 The proposed research is a collaborative study involving the Eastern Maine Medical
97 Center Weight Management Program. This program currently has no formal physical
98 activity recommendation for its non-surgical participants. The Weight Management
99 Program managers are seeking guidance as to successful physical activity
100 recommendations for their patients. It is anticipated that a wide demographic will be
101 represented allowing the results to be applied across the spectrum of age and gender.

102 Objectives:

103 1. Identify any difference in the functional outcome measures resulting from
104 participation in the different forms of physical activity

105 2. Identify differences in compliance among the various types of physical activity with
106 the supervised group and individual sessions.
107 3. Determine the impact of the type of physical activity on the health measures
108 collected including blood pressure, and weight.
109 4. Identify differences in self-reported quality of life measures resulting from
110 participation in the different physical activities.

111

112

113 Clearly, an intervention that would reduce mobility deficits in this population and
114 improve overall health could have a tremendous impact on quality of life for a large
115 portion of the population. The overarching aim of the proposed study is thus to help
116 identify a beneficial and feasible program to impact activity level and therefore health
117 and well-being of people with morbid obesity.

118 **PARTICIPANT RECRUITMENT AND SELECTION:** Participants will be recruited from the Eastern
119 Maine Medical Center Weight Management practice in Bangor, Maine. The anticipated number
120 of participants will be 45 with 15 participants in each of 3 groups. Adult clients will be included
121 if they are at least 21 years old with no restriction on upper age range. Male and female clients
122 will both be included. Inclusion criteria are as follows: Body mass index (BMI) greater than 40,
123 as determined by the physician's office, and successful performance on the Four Square Step

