124 Test balance assessment at pre-screening to determine falls risk (described below), and the
125 ability to walk independently (with or without an assistive device) for at least 50 feet.
126 Participants must also be able to attend at least one supervised session at Husson University per
127 week for 8 weeks. Data will be included in our analysis if a person has attended at least half of
128 the supervised sessions. Exclusion criteria include: history of bariatric surgery; history of
129 neurological condition (stroke, brain injury, etc.); high fall risk (as indicated by pre-screening);
130 absence of medical clearance received from the physician's office; inability to consistently
131 attend exercise sessions; and pregnancy.

132 **LOCATION:** Participants will continue to attend routine physician appointments while enrolled
133 in the Weight Management Program at Eastern Maine Medical Center during the study for
134 medical monitoring and diet consultation. The proposed study does not modify any interaction
135 with the patient's current medical management. The Tai Chi and General Exercise groups will
136 meet once a week for 8 weeks at the Kenduskeag Laboratory on the campus of Husson
137 University in Bangor, Maine, along with 2 additional sessions for pre and post testing.
138 Participants will perform the exercises or Tai Chi forms at their homes or at another location of
139 their choice 2 additional times per week. Participants in the control group will also attend 2
140 sessions at the Kenduskeag Laboratory for pre- and post-testing; the remainder of their
141 participation will occur at a location of their choice. Functional outcome data, anthropometric
142 measures, height, weight, and vital signs will also be collected at the Kenduskeag Laboratory.

143 **DURATION:** The supervised exercise sessions will take place for 8 consecutive weeks.
144 Following the 8-week intervention, the participants will return for reassessment of the outcome
145 measures; thus each participant's time involvement in this study will be approximately 10 weeks
146 (including pre and post testing). We anticipate that this study will be done in two consecutive
147 phases, each spanning approximately one academic year, with the entire study taking place
148 between August of 2016 and May of 2018. The first phase of the study will include participants
149 who are in the Tai Chi group and a control group, and the other phase will include those who are

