202 rises is recorded. Lastly, the researchers will ask the participants to walk down a Zeno walkway,
203 which is an instrumented 20-foot pad that records gait parameters electronically. The

204 researchers performing the outcome measures data collection will be blinded to the group
205 assignment of the participants.

206 The groups of participants will include two intervention groups and two corresponding control
207 groups. The control groups will receive the instruction in participation in physical activity
208 currently provided by the Weight Management Program, but will receive no formal interaction
209 with an exercise instructor or physical therapist during the study period. This is the current
210 standard protocol, so no treatment is being withheld from this group of participants. One
211 intervention group will be instructed in Tai Chi exercises during weekly supervised exercise
212 sessions. A commercially available DVD will be utilized to lead the exercise session with close
213 supervision of technique and safety by the assigned researchers. Participants in this group will
214 be provided with an identical Tai Chi DVD to use during their home sessions. The DVD was
215 created by [name], a Tai Chi master who is also a medical doctor, and is specifically geared
216 towards people with arthritis who want to enjoy Tai Chi. We chose this because we could not
217 find a DVD that had been developed for people with obesity, and since many obese people
218 would also benefit from joint protection techniques, we felt that the modifications the master
219 has made for this population would be appropriate for our targeted research participants.

220 Following completion of the 8-week study period, the people who were assigned to the
221 corresponding control group will be offered a 4-week supervised Tai Chi program along with the
222 accompanying DVD. We hope that this will help provide an incentive for them to return for the
223 second measurement session, and will also reward them for participating as part of the control
224 group.

225 In the second phase of the study, a group will be instructed in an exercise program of resisted
226 exercises for trunk, upper and lower extremities and stretching exercises. These participants
227 will attend one supervised session per week and will have a DVD to use at home to remind them

228 of the exercises. This DVD will be created and produced by the researchers specifically for this

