229 population, based on their knowledge of exercise. Resistance to the exercise will be achieved by
230 the use of elastic bands with varying amounts of resistance. Resistance will be increased during
231 the supervised exercise sessions, as appropriate, on an individual basis. The exercises will
232 become progressively harder over the 8-week period. An additional control group will be
233 recruited as a comparison for this resistance exercise group. The addition of a control group for
234 this phase of the study will allow the researchers to be blinded as they take measurements, and
235 will allow each phase of the study to stand on its own as a complete project with a valid
236 comparison group. After the 8-week study period is completed and post-study measurements
237 have been completed, the control group participants will be offered a 4-week supervised
238 exercise session of resistance training. As described above, this should provide incentive to
239 return for the second measurement session, and will serve as a reward for their participation.

240 All of the group exercise sessions will be supervised and led by student physical therapists, with
241 a licensed physical therapist (one of the co-investigators) present at all times. The students and
242 physical therapists are well trained in identifying and guarding patients who may be at risk for
243 falls, though the initial screening should have identified these people and allowed us to exclude
244 them from the study. Prior to starting the exercise sessions with the participants, the
245 researchers will attend instructional sessions with a local experienced Tai Chi teacher ([name]
246 [name]) to learn the correct positions and movements in order to provide effective supervision.

247 During the exercise sessions, the researchers will be observing the participants closely and
248 suggesting modifications in Tai Chi forms or resistance exercises when appropriate, according to
249 the participant's individual abilities. In this sense, the Tai Chi and the resistance exercises will be
250 tailored to the appropriate level for the individual.

251 Participants in both intervention groups will be instructed to carry out a home program twice a
252 week that is similar to what they have done in the supervised session. In addition to the group
253 and individual exercises in which two groups will participate, all study participants will be

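### The only rule on whose data are analysed cannot be applied to controls, so in practice it removes only low-attending exercisers after group assignment

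*Combined protocol and SAP*

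**What the plan says.** All places are in the Combined protocol and SAP.

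- **Participant Recruitment and Selection** gives the rule: "Data will be included in our analysis if a person has attended at least half of" the supervised sessions. The planned size is in the same section: "of participants will be 45 with 15 participants in each of 3 groups". The exclusion list includes "absence of medical clearance received from the physician's office; inability to consistently" attend exercise sessions.
- **Location** has the Tai Chi and exercise groups meeting once a week for 8 weeks, with pre- and post-testing visits on top and two home sessions a week. Controls attend two "sessions at the Kenduskeag Laboratory for pre- and post-testing; the remainder of their" participation takes place elsewhere.
- **Research Design** describes the groups: "The groups of participants will include two intervention groups and two corresponding control" groups. Controls get the physical activity instruction "currently provided by the Weight Management Program, but will receive no formal interaction" with an instructor or therapist in the study period. Their 4-week programme is offered only afterwards. A control group in the second phase "will allow each phase of the study to stand on its own as a complete project with a valid" comparison group.
- **Objectives**, item 2: "2. Identify differences in compliance among the various types of physical activity with" the supervised and individual sessions.
- **Data Collection** names repeated measures ANOVA. It gives no analysis set, no handling of missing post-tests and no separate set for compliance. The data collection form has lines for sessions attended and for independent exercise.

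Nothing in the text available for review restores an analysis of everyone assigned.

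**The concern.** The rule uses behaviour that is known only after assignment, and it can act on one side only. An exerciser who attends 3 of 8 sessions is dropped. A control with the same motivation, health or spare time stays, because there is nothing for that person to miss. If such traits also go with better change scores, the retained exercisers look better than the controls even when exercise does nothing.

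The second stake is Objective 2. The study calls itself a feasibility study and compares compliance between programmes. The phrase about inclusion in the analysis is unqualified. If it covers compliance as well, the people who show that a programme was hard to keep up are removed before compliance is measured.

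**Working it through.** **1. Can the rule be applied to each group?**
- Exercise groups: 1 session a week × 8 weeks = 8; half is 4.
- Controls: 0 supervised sessions in the study period, so half of the sessions attended is 0/0. The testing visits do not help, because the plan lists them separately from the weekly sessions. The later 4-week programme does not help, because it follows the post-test.
- Read as 4 of 8, the rule would exclude every control, which contradicts the stated purpose of the control groups. Read as trivially met, it keeps every control. Only the second reading is workable.

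**2. Size of the shift with no true effect**

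Inputs: 15 per group is the plan's figure (3 × 15 = 45). The share dropped, p, and the within-group correlation r between attendance and change not caused by exercise are **assumptions**.

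- λ = φ(z_p)/(1−p), and shift = r·λ in SD units.
- Variance of the retained exercisers = 1 − r²λ(λ − z_p).
- Type I error comes from a noncentral t with n = 15(1−p) exercisers v 15 controls, two-sided 5%.

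Example, p=0.30 and r=0.5: λ = 0.3477/0.70 = 0.497; shift = 0.5 × 0.497 = 0.248; variance = 1 − 0.25 × 0.497 × (0.497 + 0.524) = 0.873. The noncentral t gives 9.3%. Simulation, where the number dropped varies, gives 8.9-9.0%.

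| p dropped | λ | Shift, r=0.3 | Type I | Shift, r=0.5 | Type I |
|---|---|---|---|---|---|
| 0.05 | 0.109 | 0.033 | 5.1% | 0.054 | 5.2% |
| 0.10 | 0.195 | 0.058 | 5.3% | 0.097 | 5.8% |
| 0.20 | 0.350 | 0.105 | 5.8% | 0.175 | 7.3% |
| 0.30 | 0.497 | 0.149 | 6.5% | 0.248 | about 9% |

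At r=0 the shift is 0. At r=−0.3 it has the size shown for r=0.3 and the opposite sign. If the 15 controls are spread evenly over the two phases (7-8 each), type I error at 20-30% dropped is 5.5-6.1% (r=0.3) or 6.5-8.1% (r=0.5).

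**3. How much of this is due to the rule itself?**

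The ANOVA already loses anyone without a post-test. If half of the low attenders have none, the shift without the rule is r·φ(z_p)/(2−p), so the rule adds r·φ(z_p)/[(1−p)(2−p)]. For p=0.30 and r=0.5 that is 0.5 × 0.3477/(0.70 × 1.70) = 0.146 SD. Over r=0.3-0.5 it adds 0.02-0.05 SD at 5-10% dropped and 0.06-0.15 SD at 20-30%. If all low attenders miss the post-test, it adds 0.

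**4. Which p is plausible?**

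Under a simple binomial with 8 sessions, the share attending fewer than 4 is 1.0% at 80% average attendance, 5.8% at 70% and 17.4% at 60%. These rates are assumed too.

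**5. Objective 2, if the rule governs it**

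Recorded supervised attendance can then only be 4 to 8. The examples below show that the effect on a difference between groups has no fixed direction.
- Suppose early quitters attend 1 session and everyone else attends 7. With 20% quitters, mean attendance is (0.8×7 + 0.2×1)/8 = 72.5%. With 40% it is (0.6×7 + 0.4×1)/8 = 57.5%. After filtering both groups show 7/8 = 87.5%, so a gap of 15 points becomes 0.
- Suppose 20% of each group attend 1 session and the rest attend 8 v 6. The means 6.6 v 5.0 (gap 1.6) become 8 v 6 (gap 2.0).

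**The case against.** **The loss may be small.** Participants must be able to attend weekly, and people who cannot attend consistently are excluded. This stands, and it makes 5-10% dropped the case best supported by the text. Against the roughly 1.06 SD that 15 v 15 can detect with 80% power at two-sided 5%, a shift of 0.03-0.10 SD is minor. Screening for ability to attend does not guarantee attendance, however, and the rule itself anticipates shortfalls.

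**A minimum-attendance set is a legitimate choice.** Objectives 1 and 4 ask what results from participating, and this is a pilot. This also stands. The fault is that the set is the only one, is unlabelled, and works on one side.

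**The control problem is a drafting gap.** Largely true. A reader might infer that the plan discards all controls; its stated purpose for the control groups rules that out. The one-sided filter remains once the gap is closed in the obvious way.

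**Objective 2 may not use this set.** The documents do not say. A reader might infer that the compliance objective is already defeated, but the text supports only the conditional statement. The exercise log and the data form mean that much of what is needed for a full compliance report is already planned.

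**Conclusion.** The point holds as a one-sided, post-assignment filter with a small likely effect, worth correcting before analysis. With 5-10% of exercisers dropped, the exercise-control comparison moves by about 0.03-0.10 SD and type I error is 5.1-5.8%. At the most adverse setting examined (30% dropped, r=0.5, a strong assumption) the figures are about 0.25 SD and 9%. These are upper figures for the rule's own contribution, because low attenders may also lack a post-test.

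A reader might infer that the trial's results will be biased in favour of exercise. The documents do not support that: they give neither p nor r, the shift is nil at r=0 and it reverses at negative r. For Tai Chi v resistance both groups are filtered, so the direction is unknown. What the documents do establish is that the rule cannot be applied to controls as written, and that the set for Objective 2 is unspecified. If the rule does govern Objective 2, poor supervised attendance is hidden by construction.

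**What to change.** Replace the inclusion sentence with text such as:

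> All eligible participants who passed the FSST screen and were assigned to a group, including controls, are included in their assigned group whatever their attendance. The post-test is sought from everyone, including those who stop exercising. The repeated measures ANOVA uses all participants with both a pre-test and a post-test; the number of missing post-tests and the reasons are reported by group. Supervised sessions (of 8) and home sessions (of 16) are reported for everyone assigned to an exercise group, with supervised attendance taken from the class record. An analysis restricted to exercisers who attended at least half of the supervised sessions is a labelled sensitivity analysis.

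The 16 home sessions are 2 a week × 8 weeks. Naming the FSST screen matters because consent precedes it, so a reference to everyone enrolled could take in screen failures. The class record matters because someone without a post-test might otherwise have no attendance entered.

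Research Design also says that participants with discomfort or injury may be encouraged to stop and leave the study. That wording must be reconciled with continued outcome collection, without changing any clinical stopping rule.

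Cost: one replaced sentence, one clarification and a few extra post-test invitations. The estimated effect may be slightly smaller because non-adherers are included. Limit: the documents describe no randomisation, so this avoids adding selection but does not make the groups comparable.

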254 instructed to walk daily for exercise, as per the current protocol. All participants will maintain
255 an exercise log to track their compliance with the home program and any additional activity they
256 perform, including walking. They will be instructed to stop exercising if they experience
257 significant shortness of breath, chest pain, dizziness, leg pain, or joint pain. They will be
258 instructed in the use of the BORG Rating of Perceived Exertion (RPE) Scale (Figure 3) with a
259 target range of 12-16. The Borg RPE Scale is a simple scale that allows an individual to quantify
260 his or her response to exercise. A rating of 12-16 encompasses a level of exercise that is rated
261 subjectively as “somewhat hard.” To increase safety in the home exercises, our participants will
262 be instructed to perform the exercises or Tai Chi forms near a support such as a chair, counter,
263 or railing that could be used for assistance in the event of a loss of balance. Participants may be
264 encouraged to discontinue the exercise and exit the study if they experience any discomfort or
265 injury as a result of participation.

266 **POTENTIAL RISKS:** There is always a risk related to falls and/or musculoskeletal injuries as a
267 result of participation in daily activity. There is an increased risk of falls associated with the Tai
268 Chi group due to the type of exercise and movement that is required with that activity. The FSST
269 was selected as a fall risk screening tool because of the similarity in activity between the FSST
270 and the Tai Chi positions. Thus people who can perform adequately on the FSST should be able
271 to safely perform the Tai Chi positions. These positions, while providing a challenge to balance,
272 should not be so difficult for participants that they will provoke a fall. Tai Chi is performed with
273 slow, controlled movements as well which will allow the participants to attend to their balance
274 as they perform the movement patterns. Additionally, all exercises (Tai Chi and resistance

275 exercises) will be performed at a supervised exercise session before a participant will be
276 performing them at home, which will allow the researchers to ensure that they are being
277 performed correctly and safely. During these exercise sessions, researchers will be present for
278 guarding to prevent falls. The exercises will be modified on an individual basis as necessary for

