279 safe performance at home. Participants will be instructed to perform the exercises near a
280 support during their home session in the event that they would need a balance assist.

281 Participants in all groups will be instructed in safe levels of exercise and when to stop activity.
282 They will be instructed to stop exercising if they experience shortness of breath, dizziness, leg
283 pain, chest pain, or joint pain. Since walking is the common activity that is being encouraged,
284 safety with walking will be emphasized. Walking is presently a part of the program at Eastern
285 Maine Medical Center Weight Management, and thus will not increase the patient's risk level
286 above the current protocol.

287 Any time an individual begins an exercise program, or increases the intensity of an exercise
288 program, there is a risk of mild to moderate muscle soreness. This is expected and does not
289 cause alarm. This should resolve within 2-3 days of initiating the activity, but may return again
290 when new exercises are added to the program.

291 There have been some reports of the exercise bands breaking while patients are using them,
292 which may lead to injury. The Theraband company, which fabricates the elastic bands we will
293 be using, recommends that users inspect them for tears before use, and inspect them for color
294 fading, which could indicate weakness. Recommendations also include use of a stabilizing
295 component that they manufacture, so that the band cannot slip out of a doorway. Participants
296 will be provided with new elastic bands on a regular basis to prevent breakage from wear and

297 tear. In addition, they will be educated on how to inspect their bands for age or wear and tear,
298 in order to avoid injury.

299 **POTENTIAL BENEFITS:** Physical activity has been shown to be an important element for weight
300 loss and improved physical condition. The participants in all groups stand to benefit from the
301 increased activity from the walking program. The experimental groups may see benefits in
302 strength, balance, and overall fitness level. Although the duration of the study is brief, the
303 participants may also benefit from weight loss and improvement in the results from their
304 medical exam. Participants may benefit psychologically from exercising, and those involved in
305 the two intervention groups may benefit psychologically from the group activity. The results of

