306 this study may provide guidance towards improving mobility and health in people who are
307 morbidly obese.

308 **DATA COLLECTION:** Measurements will be taken on one session prior to, and on one session
309 following completion of the 8 weeks of exercise sessions. A sample data collection form is found
310 on page 31. The participant identification numbers will be the only identifying information
311 utilized during data collection and analysis. Records of the identification codes for the
312 participants will be kept by the primary investigators only, and will be stored in hard copy in
313 their locked offices, and on their password-protected computers. These codes will be stored in
314 a separate file from the research data, so that if there were a breach of the computer, the
315 identity codes would not be obvious. Any data created and collected on paper by this study will
316 be kept in the locked offices of the primary investigators. The paper data will be transferred to
317 spreadsheets on the computers of the primary investigators, which are password
318 protected. When the data are transferred to the electronic spreadsheets, only the numerical
319 codes will be used, so even if there were a breach of the computer, individual identities would
320 not be revealed. The researchers who are assigned to collect pre-test and post-test outcome

321 measures will be excluded from participation in the exercise class instruction for all groups in
322 order to maintain blinding of the researchers. The data will be analyzed using SPSS software.
323 Analysis of the test results among the test groups will include repeated measures ANOVA to
324 compare performance on the outcome measures from initiation of the exercise program to the
325 conclusion.

326 **FUNDING:** A small internal grant from Husson University will cover the cost of the DVDs and the
327 resistance equipment required for the resistance training group. No additional funding will be
328 necessary. The exercise sessions will be monitored by students who are receiving course credit
329 and therefore do not receive reimbursement for their time, and the faculty members who will
330 be present are required to carry out this research as part of their teaching loads.

331 CONSENT FORM: See attached Informed Consent Form. This form has a Fleish-Kincaid
332 readability level of 9.0. All researchers will be instructed as to how to properly administer an

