526
527 If yes, please describe
528 _____
529 _____
530
531
532 5. What prescription medications are you taking?
533
534
535
536 6. Do you use an assistive device such as a walker or a cane to help you while
537 walking?
538
539
540
541
542

543 7. How many falls have you had in the past year, approximately? _____

544

545

546 When did those falls occur? _____

547

548

549 8. How long does it take you to get from you home to Husson? _____

550

551

552

553 9. What is your primary reason for participating in this study? _____

554

555 _____

556

557

558 10. What is your occupation? _____

559

560

561

562 11. How many hours per week do you work? _____

563

564

565

566

567

568
569**Data Collection Form:**

| | Pretest |
|---|---------|
| Participant ID number: | |
| Anthropometric Data: | |
| Height | |
| Weight | |
| BMI | |
| Neck Circumference | |
| Physical Outcome Measures: | |
| FSST (Time) | |
| 6 Minute Walk test | |
| Blood Pressure | |
| Heart Rate | |
| Distance | |
| 30 Sec Sit to Stand (#) | |
| TUG Score (time) | |
| Gait Measures | |
| Gait speed | |
| Step length | |
| Step width | |
| Double limb support time | |
| Cadence | |
| Paper and pencil surveys | |
| SF-36 Score | |
| Rapid Assessment of Phys Activ | |
| Number of sessions attended at Husson | |
| Number of times exercised independently | |

570
571

572

Data Collection Form:

573

| | Post test |
|---|-----------|
| Participant ID number: | |
| Anthropometric Data: | |
| Height | |
| Weight | |
| BMI | |
| Neck Circumference | |
| Physical Outcome Measures: | |
| FSST (Time) | |
| 6 Minute Walk test | |
| Blood Pressure | |
| Heart Rate | |
| Distance | |
| 30 Sec Sit to Stand (#) | |
| TUG Score (time) | |
| Gait Measures | |
| Gait speed | |
| Step length | |
| Step width | |
| Double limb support time | |
| Cadence | |
| Paper and pencil surveys | |
| SF-36 Score | |
| Rapid Assessment of Phys Activ | |
| Number of sessions attended at Husson | |
| Number of times exercised independently | |

574

575

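### Stopping the exercise and leaving the study are treated as one step, with no post-test described for leavers and no field for in-study falls or injuries on the data collection forms

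*Combined protocol and SAP*

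**What the plan says.** The last sentence of RESEARCH DESIGN says that participants may be "encouraged to discontinue the exercise and exit the study if they experience any discomfort or" "injury as a result of participation". It does not say whether someone who leaves this way is asked back for the post-test, or whether the reason is written down.

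POTENTIAL RISKS says that when someone starts or steps up an exercise "program, there is a risk of mild to moderate muscle soreness. This is expected and does not" cause alarm. It adds that soreness should settle in 2-3 days and may come back when exercises are added. The same section says of the Tai Chi group: "There is an increased risk of falls associated with the Tai". It also foresees injury from elastic bands that break.

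DATA COLLECTION gives two measurement occasions: "Measurements will be taken on one session prior to, and on one session" after the 8 weeks. The analysis named is a repeated measures ANOVA, with no rule for missing data. PARTICIPANT RECRUITMENT AND SELECTION adds a filter: "Data will be included in our analysis if a person has attended at least half of" the supervised sessions.

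The demographic form asks at item 7: "How many falls have you had in the past year, approximately". The pretest and post-test data collection forms end with counts of sessions attended and of independent exercise. Neither has a row for falls, injuries or reason for stopping. RESEARCH DESIGN describes the exercise log as a record of compliance and activity.

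**The concern.** Whether a person goes on exercising and whether that person is measured at the end are separate decisions. The plan joins them, and the trigger is any discomfort or injury from participation. Read literally, that includes the soreness that POTENTIAL RISKS calls expected.

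A person who leaves has no post-test and contributes no change to the pre/post comparison. If people who do badly with the exercise are more likely to leave, the mean among those who stay is too favourable. Exits caused by the exercise should be more common where there are classes and a home programme, that is, in the Tai Chi and resistance groups.

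The plan also expects some harms, but its data collection forms give no place to record them. The study seeks a beneficial and feasible activity programme, so tolerability is a central result. A report of no falls would not show whether there were none or none were written down.

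**Working it through.** The plan gives no drop-out rate, SD, effect size, alpha or power, so it has no figure of its own to reproduce beyond 3 × 15 = 45. The check is mainly of the text; the arithmetic illustrates size.

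**1. Who is measured after stopping.** The exit sentence removes the person from the study. DATA COLLECTION has one post-test and describes no visit for early leavers. A repeated measures ANOVA on two occasions needs both values from each person.

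**2. How this relates to the attendance rule.** Half of 8 weekly sessions is 4. Someone who exits after 3 sessions is outside the analysis set even if a post-test is obtained. Someone who exits after 5 sessions passes the rule but may have no post-test. The two routes of loss overlap for early exits and differ for later ones, so mending one alone leaves the other.

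**3. Where an in-study fall or injury could be recorded.**
- Demographic form, item 7: past-year falls at entry only.
- Pretest and post-test forms: no field.
- Exercise log: described for compliance and activity; its layout is not shown.

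**4. Illustrative bias in an exercise group.** Let n = 15 (PARTICIPANT RECRUITMENT AND SELECTION), let k people exit, let m be the mean change in those who stay, and let the leavers' mean change be D SD worse.

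Full-group mean = [(n − k)m + k(m − D)] / n = m − (k/n)D.

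Overstatement = (k/n)D. Both k and D are assumptions:

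| k of 15 | D = 0.5 SD | D = 1.0 SD |
|---|---|---|
| 2 | 0.07 | 0.13 |
| 3 | 0.10 | 0.20 |
| 4 | 0.13 | 0.27 |

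These values carry over to the between-group difference only if controls have no matching loss. In general the net bias is (exercise share lost × D in exercisers) − (control share lost × D in controls). With one fifth lost and D = 1.0 on both sides it is 0.20 − 0.20 = 0.

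**5. Scale.** At an assumed 80% power and two-sided 5% alpha, the normal approximation gives a detectable difference of 2.802 × √(1/15 + 1/15) ≈ 1.03 SD for 15 v 15. For 12 v 15 it is 2.802 × √(1/12 + 1/15) ≈ 1.09 SD (both rounded up). Losing three people costs little power, so the issue is bias and missing harms.

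**6. Harms.** If 3 of 15 left injured and unrecorded, the data would show 0 of 12 where the truth is 3/15 = 20%. Even a fully recorded 0 of 15 has an exact two-sided 95% upper limit of 1 − 0.025^(1/15) = 21.8% (one-sided: 1 − 0.05^(1/15) = 18.1%).

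**The case against.** The strongest reply is that the plan is milder than the concern suggests. The clause is permissive, RESEARCH DESIGN provides for exercises to be modified individually, and nothing bars a post-test for someone who only stops exercising. Much of this stands, and it rules out several stronger readings that a reader might infer.

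- *That no form records falls.* Item 7 of the demographic form does, for the year before entry. What is missing is an in-study field on the forms shown. The data collection form is called a sample, and the log layout and consent form are not in the text reviewed.
- *That poor responders will disappear from the results.* Loss is an inference from the exit clause, the single post-test and the lack of a missing-data rule. It may happen; the documents do not say that it will.
- *That most exercisers would meet the trigger.* No figure supports this. Soreness is called expected and short-lived, and the clause can be read as not covering it. What remains is that the two statements need reconciling.
- *That loss falls mostly in one arm and favours exercise.* More exits for exercise-related discomfort in the exercise groups are plausible. But controls also walk daily and keep a log, and the retention worry that the plan voices is about controls, who are offered a 4-week programme partly so that they return. The net imbalance is unknown.
- *That nothing clinical would keep someone who stops from the post-test.* The documents do not establish this. The post-test includes a 6-minute walk, sit-to-stand and stepping tests, which an injured person may be unable to do.

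None of this supplies a follow-up for leavers or an in-study harms field.

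**Conclusion.** The concern holds in a limited form. As written, the plan lets people leave the study for exercise-related discomfort or injury, describes no post-test for them, and has no field on the data collection forms shown for falls, injuries or reason for stopping during the 8 weeks. Outcomes may be lost for people who tolerate the exercise poorly, and harms may be under-counted.

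The size cannot be derived from the documents. The range of 0.07 to 0.27 SD in favour of exercise rests on three assumptions: 2 to 4 exits of 15, a change 0.5 to 1.0 SD worse in leavers, and no matching control loss. Loss of controls who were also doing worse would shrink or cancel it. The gap in harms recording does not depend on these assumptions. For a pilot study this should be changed, but it does not undermine the design.

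**What to change.** 1. The sponsor reconciles the exit sentence in RESEARCH DESIGN with the soreness paragraph in POTENTIAL RISKS. When exercise should stop remains the sponsor's decision.
2. State that stopping the exercise does not by itself end study participation. Invite everyone enrolled to the existing post-test, for whichever measures they can safely do, unless consent is withdrawn.
3. Analyse everyone in the assigned group, and amend the half-attendance rule to match, for example by keeping it only as a sensitivity analysis. Otherwise an early stopper who returns is still excluded.
4. For all groups, record falls, injuries and reason for stopping during the study in the exercise log or a class record, and by a self-completed item or a call to those who do not return. A row on the post-test form alone would miss the non-returners.
5. Have staff other than the blinded assessors handle these items, because a reason for stopping can reveal the group. The sessions-attended row on the post-test form already carries that risk.
6. Report exits, reasons and events by group.

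The cost is a few sentences, a few log or form items and some reminder calls; the post-test visit already exists. Post-tests from people who stopped exercising may dilute the apparent effect.
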